5.7. Pharmacokinetic Analysis

The serum concentrations will be evaluated for nanrilkefusp alfa analyte and may or may not be evaluated for the cetuximab analyte (cetuximab samples will be collected to be analyzed later during the course of the study, if needed). Serum samples will be collected from all patients in the initial safety cohorts and from the first 12 patients in the main study cohort. The actual date and time (24-hour clock time) of each serum sample will be recorded.

The following PK parameters will be determined where possible from the serum concentrations of nanrilkefusp alfa using non-compartmental methods in the validated software program Phoenix WinNonlin (Certara, Version 8.3.5 or higher):

Parameter	Definition
AUC_{last}	area under the concentration-time curve over the last measurable concentration (T_{last}) (Cycle 1 Day 1 only)
$AUC_{(0-4h)}$	area under the concentration-time curve over time 0 to 4 hours postdose (Cycle 1 Day 1 only)
$AUC_{(0-24h)}$	area under the concentration-time curve over time 0 to 24 hours postdose (Cycle 1 Day 1 only)
C_{max}	observed maximum concentration (Cycle 1 Day 1 only)
C_{2h}	observed concentration at 2 hours postdose (Cycle 1 and 3 Days 1)

Parameter	Definition
C_{trough}	observed trough concentration (Cycle 1 Day 2 predose = Cycle 1 Day 1 trough; Cycle 1 Day 9 predose = Cycle 1 Day 8 trough; Cycle 3 Day 1 predose = Cycle 2 Day 9 trough)
T_{max}	time to maximum concentration (Cycle 1 Day 1 only)
T_{last}	time of the last measurable concentration (Cycle 1 Day 1 only)
R_{C2h} , and $R_{C_{trough}}$	Accumulation Ratio of C_{2h} on Cycle 3 Day 1/Cycle 1 Day 1 Accumulation Ratio of C_{trough} on Cycle 2 Day 9/Cycle 1 Day 1

For the Cycle 1 Day 1 profile, the Cycle 1 Day 2 predose concentration will be the 24 hour timepoint.

If cetuximab concentrations are available, C_{trough} will be reported for Cycle 1 (predose concentration on Day 8 and 15) and Cycle 3 (predose concentration on Day 1).

Additional PK parameters may be determined where appropriate.

The units of the PK parameters will be based on the concentration units provided by the bioanalytical laboratory and the dose units used in the study.

Pharmacokinetic analysis will be carried out where possible using actual dose administered (μg for nanrilkefusp alfa) and actual postdose blood sampling times. If an actual time is missing, the sample concentration result will be treated as missing unless there is scientific justification to include the result using the nominal time.

The parameters C_{max} , C_{trough} , C_{2h} , T_{last} , and T_{max} will be obtained directly from the concentration-time profiles. If C_{max} occurs at more than 1 timepoint, T_{max} will be assigned to the first occurrence of C_{max} .

The area under the concentration-time curve (AUC) parameters will be calculated using the linear trapezoidal rule for increasing concentrations and the logarithmic rule for decreasing concentrations (linear up/log down rule).

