- 21. Samples for Fc gamma receptor polymorphism only in cycle 1
- 22. Contact 90 (± 2) days after the last dose of nanrilkefusp alfa and/or cetuximab (whichever occurs later) and then at 3-month (± 2 weeks) intervals until the end of the study

Table 1.1: Pharmacokinetic sampling

Serum samples will be collected from all patients in the initial safety cohorts and from the first 12 patients in the main cohort. All attempts should be made to collect the samples on time.

Cycle, day	Time point	Nanrilefusp alfa	Cetuximab
Cycle 1 day 1	Pre-dose to nanrilefusp alfa and cetuximab	X	X
	30 min (± 5 min)	X	
	1 h (± 5 min)	X	
	2 h (± 15 min)	X	X
	4 h (± 30 min)	X	X
	12 h (± 2 h), if logistically possible	X	
Cycle 1 day 2	Pre-dose to cycle 1 day 2 nanrilefusp alfa ¹ (-2 h [-15 min] to 0 h)	X	
Cycle 1 day 8	Pre-dose to cycle 1 day 8 nanrilefusp alfa and cetuximab ¹ (-2 h [-15 min] to 0 h)	X	X
Cycle 1 day 9	Pre-dose to cycle 1 day 9 nanrilefusp alfa ¹ (-2 h [-15 min] to 0 h)	X	
	2 h (± 15 min)	X	
	4 h (± 30 min)	X	
Cycle 1 day 15	Pre-dose to cycle 1 day 15 cetuximab ¹ (-2 h [-15 min] to 0 h)		X
Cycle 3 day 1	Pre-dose to nanrilefusp alfa and cetuximab ¹ (-2 h [-15 min] to 0 h)	X	X
	2 h (± 15 min)	X	X

¹ Sample to be taken as early as possible when patients arrive at site

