6.1 Study interventions administered

The interventions to be administered in this study are listed in [Table 6.1](#).

Prophylactic antibiotic therapy (e.g., oral lymecycline or doxycycline) to prevent EGFR inhibitor-related skin toxicities are permitted according to local guidelines.

Prior to the first infusion of cetuximab, patients may receive premedication with an antihistamine and a corticosteroid at least 1 hour prior to administration of cetuximab. This premedication is recommended prior to all subsequent infusions.

Nanrilkefusp alfa subcutaneous injection sites will be rotated to different areas of the body (upper and lower extremities, each of the 4 quadrants of the abdomen) to minimize the summated local effects of nanrilkefusp alfa administration.

The pharmacy manual contains specific instructions for the preparation of the nanrilkefusp alfa dose and cetuximab infusion and administration of nanrilkefusp alfa and cetuximab.

Table 6.1: Study interventions

Intervention name and type	Dosage formulation	Unit dose strength(s)	Dosage level(s)	Route of administration	Regimen/ treatment period	Sourcing
Nanrilkefusp alfa Investigational intervention	Solution for injection	1.3 mg/vial	See section 4.1.1	Subcutaneous	Administration on day 1 (from cycle 2 onwards, ± 1 day), day 2 (± 1 day), day 8 (± 1 day), and day 9 (± 1 day) of each 21-day cycle	Provided centrally
Cetuximab Investigational intervention	Solution for infusion	5 mg/mL	Initial dose: 400 mg/m ² body surface area as intravenous infusion over 120 minutes Subsequent doses: 250 mg/m ² as intravenous infusion over 60 minutes	Intravenous infusion via peripheral or central venous line	Administration on day 1 (from cycle 2 onwards, ± 1 day), day 8 (± 1 day), and day 15 (± 1 day) of each 21-day cycle; on day 1 and day 8, cetuximab infusion will start within 30 minutes after nanrilkefusp alfa administration	Provided centrally

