8.3.8.4 Report forms

The SAE Report Form, **primarily completed within the eCRF system** for the study, will be used for reporting of SAEs and submitted to the sponsor or designee. In case the eCRF system is not available/accessible, a paper SAE Report Form is filled out and sent to the sponsor or designee (see details above).

For reporting of pregnancies, the paper Pregnancy Data Collection Form is to be used. Completion guidelines provide information on format and details of the information required.

Originals of the paper report forms must be kept in the site study file.

The report forms need to be completed in English.

All immediately reportable events from the investigational site to the sponsor or designee (i.e., SAEs and patients' or partners' pregnancies) must also be recorded in the site's source documentation and on the eCRF as appropriate.

8.4 PK

The following serum PK parameters will be determined (nanrilkefusp alfa and cetuximab; cetuximab samples will be collected to be analyzed later during the course of the study if needed):

- Area under the concentration-time curve (AUC; over the last measurable timepoint [AUC_{last}], extrapolated to infinity [AUC_{inf}] and over the dosing interval [AUC_{tau}])
- Observed maximum concentration (C_{max})
- Time to maximum concentration (T_{max})
- Pre-dose concentration (C_{trough})
- Apparent terminal elimination half-life (T_{1/2})

- Apparent systemic clearance (CL) for single dose and steady state
- Apparent volume of distribution at steady state (V_{ss}) and during terminal phase (V_z)
- Accumulation ratio (R_{AUC} , R_{Cmax})

PK parameters will be generated by noncompartmental and/or compartmental approaches as appropriate. Additional PK parameters may be calculated at the discretion of the pharmacokineticist. Further details will be specified in the PK analysis plan.

The actual date and time (24-hour clock time) of each sample will be recorded.

Instructions on sample collection, handling, storage, and shipment of samples are detailed in the study-specific laboratory manual provided to the study site.

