MedDRA	Medical Dictionary for Regulatory Activities
MRI	Magnetic Resonance Imaging
NC	Not Calculated
NCI-CTCAE	National Cancer Institute-Common Terminology Criteria for AEs
NE	Not Evaluable
N-RAS	Neuroblastoma Rat Sarcoma Viral Oncogene Homolog
ORR	Objective response rate (according to RECIST)
OS	Overall Survival
PD	Progressive Disease
PFS	Progression-free Survival (according to RECIST)
PFS2	PFS on Next-line Anti-cancer Treatment
PK	Pharmacokinetic
PP	Per Protocol
PR	Partial Response
PT	Preferred Term
QTcB	Bazett Corrected QT Interval
QTcF	Fridericia Corrected QT Interval
R _{C2h} , R _{Ctrough}	Accumulation Ratio of C _{2h} or C _{trough} on Cycle 3 Day 1/Cycle 1 Day 1
RECIST	Response Evaluation Criteria in Solid Tumors
RP2D	Recommended Phase 2 Dose
SAE	Serious AE
SAP	Statistical Analysis Plan
SBP	Systolic BP
SD	Standard Deviation
SD	Stable Disease
SI	International System of Units
SOC	System Organ Class
TFLs	Tables, Figures and Listings
T _{last}	Time of the Last Measurable Concentration
T _{max}	Time to Maximum Concentration
TEAE	Treatment Emergent Adverse Event
TESAE	Treatment Emergent SAE
TtP	Time to Progression (according to RECIST)
TtR	Time to Response (according to RECIST)
ULN	Upper Limit of Normal Reference Range

1. Source Documents

The Statistical Analysis Plan (SAP) was written based on the following documentation:

Document	Date	Version
Protocol	09Mar2023	Protocol Amendment 1
eCRF	03May2023	3.0

2. Protocol Details

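### The SAP's trough accumulation ratio divides a level about 13 days after a dose by one 24 hours after a dose, so it cannot be read as accumulation

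*SAP*

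**What the plan says.** The parameter table in SAP 5.7 names two accumulation ratios for nanrilkefusp alfa. R_C2h compares the 2-hour level on Cycle 3 Day 1 with that on Cycle 1 Day 1. R_Ctrough compares troughs "on Cycle 2 Day 9/Cycle 1 Day 1".

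The same table says which sample stands for each trough. For the numerator: "Cycle 3 Day 1 predose = Cycle 2 Day 9 trough". The Cycle 1 Day 1 trough is the Cycle 1 Day 2 predose sample, and below the table the SAP adds that "the Cycle 1 Day 2 predose concentration will be the 24 hour timepoint". The Cycle 1 Day 9 predose sample is also a named trough, belonging to the Day 8 dose, but no named ratio uses it.

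Protocol Table 6.1 gives nanrilkefusp alfa on days 1 and 2 and on "day 8 (± 1 day), and day 9 (± 1 day) of each 21-day cycle". No dose falls between Day 9 and the next Day 1.

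The SAP abbreviation list describes both ratios as "on Cycle 3 Day 1/Cycle 1 Day 1", which for R_Ctrough differs from Section 5.7.

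**The concern.** An accumulation ratio compares levels at the same time after a dose, so that it equals 1 when nothing is carried over and rises above 1 when something is. R_Ctrough compares the end of a gap of about 13 days with the end of a one-day gap. Elimination over the extra days and carry-over from earlier doses are mixed in one number, and its no-carry-over value depends on a half-life that the documents do not give.

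Calculated PK parameters of nanrilkefusp alfa are a secondary endpoint, and these are the only two accumulation ratios that SAP 5.7 names. A low R_Ctrough could be reported as absence of accumulation when it shows only that the sample was late. At multi-day half-lives the two ratios could fall on opposite sides of 1 in the same patients, with nothing in the SAP to explain why.

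**Working it through.** **Times after dose.** Study day = (cycle − 1) × 21 + day.

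- Denominator: Cycle 1 Day 2 is day 2 and the dose was on day 1, so 24 h. This reproduces the SAP's own 24-hour label.
- Numerator: Cycle 3 Day 1 is day 43 and Cycle 2 Day 9 is day 30, so 43 − 30 = 13 days. With the ±1 day windows it is 42 − 31 = 11 to 44 − 29 = 15 days.
- Nominal difference: 13 − 1 = 12 days.

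This step needs no half-life. For any level that is falling between 24 h and 13 days after a dose, the ratio without carry-over is below 1.

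**Size.** The documents state no half-life, so a range is assumed: linear one-compartment kinetics, equal doses, instant absorption, half-life t in days. The doses of the first two cycles fall on days d = 1, 2, 8, 9, 22, 23, 29 and 30.

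- No-carry-over value = 2^(−13/t) / 2^(−1/t) = 2^(−12/t).
- Planned R_Ctrough = Σ 2^(−(43 − d)/t) / 2^(−1/t), over the eight doses.
- R_C2h = level 2 h after the Cycle 3 Day 1 dose, all doses counted, over the level 2 h after the first dose.
- Matched trough ratio, Cycle 1 Day 9 predose over Cycle 1 Day 2 predose = [2^(−8/t) + 2^(−7/t) + 2^(−1/t)] / 2^(−1/t).

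Example at t = 5 days: the no-carry-over value is 2^(−2.4) = 0.19. The eight terms of the planned ratio, latest dose first, are 0.1895 + 0.1649 + 0.0718 + 0.0625 + 0.0103 + 0.0090 + 0.0039 + 0.0034 = 0.515.

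| Half-life (days) | No carry-over | Planned R_Ctrough | R_C2h | Matched trough ratio |
|---|---|---|---|---|
| 1 | 0.0002 | 0.0004 | 1.00 | 1.02 |
| 2 | 0.016 | 0.03 | 1.02 | 1.21 |
| 3 | 0.063 | 0.14 | 1.11 | 1.45 |
| 5 | 0.19 | 0.52 | 1.45 | 1.81 |
| 7 | 0.30 | 0.98 | 1.89 | 2.05 |

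The planned ratio reaches 1 only at a half-life of about 7.1 days, where matched troughs have already roughly doubled.

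**Sensitivity.** With first-order absorption at 0.25 to 1 per hour, the planned ratio at 5 days stays at 0.515 to 0.517. With every ±1 day dosing and sampling window varied and doses kept in order, it spans about 0.085 to 0.27 at 3 days and 0.39 to 0.78 at 5 days.

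**Values below quantification.** SAP 5.7.2 sets them to 0 before the first measurable concentration and to missing afterwards. A Cycle 3 Day 1 predose level below the limit therefore makes the ratio either 0 or not calculable, depending on how that rule is read. Neither outcome is informative.

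**Abbreviation list.** Its wording fits R_C2h but not R_Ctrough under either reading. If the trough of a day is the next predose sample, as in SAP 5.7, Cycle 3 Day 1 would need a Cycle 3 Day 2 predose sample, and Protocol Table 1.1 schedules none. If a trough is simply a "Pre-dose concentration" on the day named, as in Protocol 8.4, the Cycle 1 Day 1 denominator precedes any drug.

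**The case against.** The strongest reply is that little is lost. The analyses are descriptive. The ratio exists only in the PK subset: all safety-cohort patients (an estimated 6 to 12) plus the first 12 of the main cohort, so about 18 to 24. The SAP states which sample is each trough, the concentrations are listed and summarised by cycle and scheduled time (SAP 5.7.4), and R_C2h already gives a matched comparison across cycles. All of this stands and keeps the point small. It does not make the ratio mean what its name says.

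The opposing-directions scenario needs a multi-day half-life, which the documents do not establish. That also stands. At half-lives of about 24 h or less the ratio is near 0 and R_C2h is near 1, so a conclusion of no accumulation would be right, but R_Ctrough would have contributed nothing to it.

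The SAP also says "Additional PK parameters may be determined where appropriate". That allows a matched ratio to be added; it does not correct the one already named. Nor does the use of actual sampling times, because troughs are read directly from the profile without adjustment for time after dose.

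Two further readings are tempting. A reader might infer that the abbreviation list differs only in its label and points to the same samples. That works only if numerator and denominator are read by different conventions. A reader might also infer that the permitted increase from 9 to 12 µg/kg distorts the Cycle 3 comparison. On the shortest timetable in Protocol 4.1.1, the third 12 µg/kg patient ends the DLT period on about day 50 of the last initial 9 µg/kg patient, after that patient's Cycle 3 Day 1 on day 43. The increase would reach that sample only if cycles slipped by about a week or more, so it is a side issue here.

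**Conclusion.** The definition is wrong as written. R_Ctrough compares samples whose nominal times after dose differ by 12 days, so it is below 1 without carry-over and should not be called an accumulation ratio. The interval mismatch follows from the documents alone. The tabulated values rest on the assumed one-compartment model and half-life range and illustrate size; they do not predict this drug's results.

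The importance is minor. A reader might infer that the trial's PK assessment, or its choice of dose, is compromised. The documents do not support that: accumulation is still assessed by a matched ratio, the concentrations are reported, and no dose, stopping or primary-endpoint rule uses R_Ctrough. The correction is worth making because the misnamed parameter sits under a secondary endpoint and is easy to put right.

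**What to change.** In SAP 5.7:

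- Stop reporting the Cycle 2 Day 9 over Cycle 1 Day 1 trough ratio as accumulation. Report Cycle 3 Day 1 predose as a residual concentration only.
- Keep R_C2h, Cycle 3 Day 1 over Cycle 1 Day 1, as the cross-cycle measure.
- If a trough ratio is wanted, define it as Cycle 1 Day 9 predose over Cycle 1 Day 2 predose. Compute it only where the actual times after dose are comparable, for example 24 h ±10%, a new rule modelled on the tolerance in SAP 5.7.1. Describe it as week-to-week carry-over within Cycle 1, and state that it is insensitive at half-lives of about 24 h or less (1.02 at 24 h). It does not replace a Cycle 3 comparison.

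In the abbreviation list, give R_C2h and any trough ratio separate definitions that match Section 5.7.

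The cost is a few lines of SAP text. Protocol Table 1.1 already schedules the sample labelled "Pre-dose to cycle 1 day 9" and every other sample needed, so no visit or blood draw is added.

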Study interventions	
Nanrilkefusp alfa will be administered subcutaneously on day 1 (from cycle 2 onwards, ± 1 day), day 2 (± 1 day), day 8 (± 1 day), and day 9 (± 1 day) of each 21-day cycle. The dose of nanrilkefusp alfa for the main cohort of the study will be determined in the initial 3+3 safety cohorts.
 
Cetuximab will be administered on day 1 (from cycle 2 onwards, ± 1 day), day 8 (± 1 day), and day 15 (± 1 day) of each 21-day cycle. The initial dose of cetuximab will be 400 mg/m^2 body surface area administered as intravenous infusion over 120 minutes. All subsequent weekly doses will be 250 mg/m^2 each administered as intravenous infusion over 60 minutes. Prior to the first infusion of cetuximab, patients may receive premedication with an antihistamine and a corticosteroid at least 1 hour prior to administration of cetuximab. This premedication is recommended prior to all subsequent infusions. On day 1 and day 8, cetuximab infusion will start within 30 minutes after nanrilkefusp alfa administration.
	
Study population	
Patients with RAS wild-type colorectal cancer as confirmed by the investigational site within 3 months prior to the first administration of study treatment who are relapsed/refractory or intolerant to prior treatment with irinotecan- and oxaliplatin-containing chemotherapy
	

Study duration	The study will end one year after the last patient's last dose of study treatment (nanrilkefusp alfa and/or cetuximab [whichever occurs later]) or 3 years after the last patient has received the first dose of nanrilkefusp alfa (whichever occurs earlier).
Estimated sample size	Approximately 52 patients

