5.7.1. Criteria for Calculation and Reporting of Area Under the Concentration-time Curve

The minimum requirement for the calculation of AUC will be the inclusion of at least 3 consecutive concentrations above the lower limit of quantification. If there are only 3 consecutive concentrations, at least 1 should follow C_{max} .

For calculation of the partial AUC parameters, if the end interval PK sample is collected slightly earlier than the nominal time, the AUC parameter will be calculated using the end interval sample if the collection is within $\pm 10\%$ of the nominal sampling time.

5.7.2. Criteria for Handling Concentrations Below the Limit of Quantification or Missing Concentrations for Pharmacokinetic Analysis

Serum concentrations below the limit of quantification (BLQ) will be assigned a value of 0 before the first measurable concentration and thereafter BLQ concentrations will be treated as missing. The following rules apply to the specific situations defined below:

- If an entire concentration-time profile is BLQ, it will be excluded from PK analysis.
- Where 2 or more consecutive concentrations are BLQ at the end of a concentration-time curve, the curve will be deemed to have terminated and any further quantifiable concentrations will be set to missing for the calculation of the PK parameters, unless they are considered to be a true characteristic of the profile of the drug.
- If a predose serum concentration is missing on the first day of dosing day (Cycle 1 Day 1), it will be set to 0 by default within Phoenix WinNonlin.

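### The Cycle 1 Day 2 predose sample is fixed as the 24 h point and Cycle 1 C_trough has no time limit, so in-window visit shifts can put 48 h (Day 9: up to 72 h) levels among 24 h values

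*SAP*

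**What the plan says.** **Labels.** SAP 5.7 fixes the Day 2 sample: "For the Cycle 1 Day 1 profile, the Cycle 1 Day 2 predose concentration will be the 24 hour timepoint". SAP 5.7.4 repeats this for all individual and summary concentration figures. For the second pair of doses the SAP gives no hour and says only "Cycle 1 Day 9 predose = Cycle 1 Day 8 trough".

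**Derivation.** C_trough, with C_max, C_2h, T_last and T_max, "will be obtained directly from the concentration-time profiles" (SAP 5.7).

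**Visit windows.** Protocol 1.1 and Table 6.1 give nanrilkefusp alfa on "day 2 (± 1 day), day 8 (± 1 day), and day 9 (± 1 day) of each 21-day cycle". Day 1 moves only in later cycles: "day 1 (from cycle 2 onwards, ± 1 day". No minimum gap between paired days is stated. Protocol Table 1.1 ties the sample to the coming dose, not to hours since the last one: "Pre-dose to cycle 1 day 2 nanrilefusp alfa".

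**Timing rules.** SAP 5.7 uses actual sampling times where possible. SAP 5.7.1 has a tolerance for partial AUCs only: "the AUC parameter will be calculated using the end interval sample if the collection is within" 10% of the nominal time. SAP 4.1.4 applies no visit windows outside tumor assessment. The outlier rule in SAP 5.7.3 concerns values that do not fit the expected profile, not sampling times.

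**The concern.** A Day 2 visit held on day 3 complies with the protocol, but the SAP would call its predose level a 24 h level. That value would enter the 24 h row of the concentration summary and the Cycle 1 Day 1 C_trough. It would also be the denominator of R_Ctrough for that patient. A Day 9 sample drawn 48 h or more after the Day 8 dose would enter the Day 8 trough in the same way. While concentrations are falling, each such value pulls the summary down and widens its spread.

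The SAP also conflicts with itself. SAP 5.7.4 plots individual figures at actual time after dose, then sets the Day 2 predose sample to 24 h in those same figures. For a 48 h sample a programmer cannot do both. The actual-time rule in SAP 5.7 sits uneasily beside the fixed 24 h assignment for the same reason.

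At stake is the description of nanrilkefusp alfa PK, a secondary objective.

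**Working it through.** **Inputs.** Cycle 1 Day 1 is fixed; Days 2, 8 and 9 are each ±1 day (Protocol 1.1, Table 6.1). The predose sample may be taken up to 2 h 15 min before the dose (Protocol Table 1.1). PK patients are the 6 to 12 in the safety cohorts (Protocol 9.5) plus the first 12 in the main cohort (Protocol Table 1.1), so 18 to 24. The documents give no half-life and no expected share of shifted visits; both are assumed below.

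**Step 1: the plan's own figure.** Hours since previous dose = (visit day − previous dose day) × 24. On schedule, Day 2 gives (2 − 1) × 24 = 24 h. With both doses at the same clock time and the predose window applied, this is 21.75 to 24 h. The 24 h label is right for an on-schedule visit.

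**Step 2: what the windows allow.** Shifts that bring paired doses together are left aside.

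- Day 2 one day late: (3 − 1) × 24 = 48 h. This is the maximum, because Day 1 cannot move in Cycle 1.
- Day 9 with one of the two visits moved apart: (10 − 8) × 24 = 48 h, or (9 − 7) × 24 = 48 h.
- Day 9 late and Day 8 early: (10 − 7) × 24 = 72 h. This is one of the nine window combinations.
- Days 8 and 9 moved together: still 24 h.

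**Step 3: sensitivity.** Assume mono-exponential decline, so C(t)/C(24) = 2^(−(t − 24)/half-life). Write r for the 48 h ratio and s for the share of patients sampled at 48 h. The arithmetic mean changes by −s(1 − r). The geometric mean is multiplied by r^s.

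| Assumed half-life | 48 h / 24 h | 72 h / 24 h | Arithmetic mean, s = 10% | Arithmetic mean, s = 20% | Geometric mean, s = 20% |
|---|---|---|---|---|---|
| 4 h | 1.6% | 0.02% | −9.8% | −19.7% | −56% |
| 8 h | 12.5% | 1.6% | −8.8% | −17.5% | −34% |
| 12 h | 25% | 6.25% | −7.5% | −15.0% | −24% |
| 24 h | 50% | 25% | −5.0% | −10.0% | −13% |

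Example for 12 h: r = 2^(−24/12) = 0.25; 0.20 × (1 − 0.25) = 0.15; 0.25^0.20 = 0.76.

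**Step 4: values below quantification (BLQ).** Under SAP 5.7.2, a BLQ value after the first measurable concentration is treated as missing for PK parameters, so a late BLQ sample would drop out of C_trough rather than lower it. The C_trough effects in the short half-life rows are therefore upper bounds. Under SAP 4.2.8, however, the same value counts as 0 in the concentration summary, where the geometric mean then becomes not calculated.

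**The case against.** **C_trough is by definition a predose level.** Protocol 8.4 defines it that way. If the next dose comes at 48 h, the level before it is that patient's real trough. This is a fair reading of C_trough taken alone. It does not rescue the 24 h label on the Day 2 sample, and it leaves a summary that mixes dosing intervals without saying so.

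**Stronger readings that the documents do not support.**

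- A reader might infer that both samples are labelled 24 h. Only Day 2 is; for Day 9 the 24 h follows from the nominal schedule.
- A reader might infer that either sample can reach 72 h. Day 2 stops at 48 h.
- A reader might infer that late levels will be averaged in. They can be, if visits move apart; the protocol asks sites to make every attempt to sample on time.
- A reader might take the two Cycle 1 troughs as the only evidence on carry-over. Table 1.1 also has Day 9 samples at 2 h and 4 h, which can be set against the same times on Day 1.
- A reader might extend the point to the AUCs. Actual times and the 10% tolerance largely protect those, provided the actual-time rule prevails over the fixed assignment.

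**The size is assumed.** This stands. The median, which the SAP also reports, would move little with 10% to 20% of patients shifted. The geometric mean would move more than the arithmetic mean as long as late values are quantifiable.

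**A strict time window could do harm.** This also stands. Dosing clock times are not fixed. A Day 1 dose at 15:00 and a Day 2 predose sample at 09:00 are 18 h apart, and a 24 h ± 10% rule (21.6 to 26.4 h) would discard that on-schedule sample.

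**Conclusion.** The point holds as a minor but real defect. The SAP fixes a compliant 48 h Day 2 sample as a 24 h level, contradicts its own actual-time rule for the figures, and sets no time criterion for the two Cycle 1 troughs.

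If decline is mono-exponential with a half-life of 4 to 24 h, a 48 h level is about 2% to 50% of the 24 h level. With 10% to 20% of patients shifted, the arithmetic mean trough would be about 5% to 20% too low. The bias in C_trough is smaller if late samples are BLQ and treated as missing. If no visits move apart, there is no bias.

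The effect is confined to descriptive PK in about 18 to 24 patients. Dose decisions rest on safety review and DLTs, and the primary ORR is untouched.

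R_Ctrough has a separate limitation that this point does not address: its numerator is taken nominally (22 − 9) × 24 = 312 h after the Cycle 2 Day 9 dose, against 24 h for its denominator.

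**What to change.** Add one rule to SAP 5.7 and refer to it in 5.7.4:

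*The Cycle 1 Day 2 predose sample is the 24 h point of the Day 1 profile, and the Day 2 and Day 9 predose samples enter the Cycle 1 C_trough and R_Ctrough summaries, only if drawn on the calendar day after the preceding nanrilkefusp alfa dose. All other samples are listed and plotted at actual time and left out of the 24 h summary.*

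A prespecified tolerance in actual hours around 24 h would also serve, if it is wide enough to keep on-schedule samples when clock times differ. Remove the sentence in SAP 5.7.4 that sets Day 2 predose to 24 h in individual figures, so that those follow actual time throughout.

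The cost is a short SAP edit. Actual sample dates and times are already recorded, and no visit, dosing or sampling rule changes. The downside is that a few patients may contribute no Cycle 1 trough; their number should be reported beside the summary.
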